#### **16.5. Study Monitoring**

Qualified representatives of the sponsor or sponsor designees (study monitors) will monitor the study according to a predetermined monitoring plan. The investigator must permit the study monitors to periodically review all eCRFs and source documents supporting the participation of each patient in the study. The eCRFs and other documentation supporting the study must be kept up to date by the investigator and the staff at the study site. These study materials must be available for review by the study monitor, and/or other qualified representatives of the sponsor, at each monitoring visit and must be provided in a way such that the patient's confidentiality is maintained in accordance with local institution, state, country, and federal requirements.

#### **16.6. Audits and Inspections**

At some point during the study or after the study, appropriately qualified personnel from the sponsor's Quality Assurance group, or their authorized representative, or a representative from a regulatory authority may visit the investigator to conduct an inspection of the study and the site. During this audit, the investigator agrees to give the auditor direct access to all relevant documents supporting the eCRFs and other study-related documents and to discuss any findings with the auditor. In the event of an inspection by a regulatory agency, the investigator agrees to give the inspector direct access to all relevant documents and to discuss any findings with the inspector.

## **17. PUBLICATION POLICY**

By signing the study protocol, the investigator and his or her institution agree that the results of the study may be used by G1 Therapeutics for the purposes of national and international registration, publication, and information for medical and pharmaceutical professionals. If necessary, the authorities will be notified of the investigator's name, address, qualifications, and extent of involvement.

Initial publication of the results of this study will be of a cooperative nature that may include authors representing the sponsor, investigator(s), and collaborating scientists. Independent publications by involved individuals may follow. Investigators and their institutions agree not to publish or publicly present any interim results of studies without the prior written consent of G1 Therapeutics.

At least 60 days prior to expected submission to the intended publisher or meeting committee, the investigator will submit a copy of the desired presentation (oral or written) or publication manuscript to the sponsor. This review period may be shortened upon mutual consent where circumstances require expeditious review. The sponsor reserves the right to request modification of any publication, presentation or use by the investigator if such activity may jeopardize a patent application, an existing patent, or other proprietary rights. The sponsor shall determine order of authorship of any publication combining all clinical results of this trial.

## **19. APPENDICES**

APPENDIX 1: Atezolizumab Guidance for the Investigator

APPENDIX 2: Package Insert for Atezolizumab

Tecentriq® (atezolizumab) injection package insert link:  
[https://www.gene.com/download/pdf/tecentriq\\_prescribing.pdf](https://www.gene.com/download/pdf/tecentriq_prescribing.pdf)

APPENDIX 3: Atezolizumab Adverse Events of Special Interest

APPENDIX 4: Package Inserts for Chemotherapy Agents

Etopophos® (etoposide phosphate) package insert link:  
[http://packageinserts.bms.com/pi/pi\\_etopophos.pdf](http://packageinserts.bms.com/pi/pi_etopophos.pdf)

Etoposide concentrate for solution for infusion 20 mg/mL. Summary of Product Characteristics July 2015 link:  
<https://www.medicines.org.uk/emc/medicine/30539>

Paraplatin® (carboplatin) package insert link:  
[http://www.fda.gov/ohrms/dockets/ac/05/briefing/2005-4180b\\_03\\_05\\_Carboplatin%20label%201-9-04%20FDA.pdf](http://www.fda.gov/ohrms/dockets/ac/05/briefing/2005-4180b_03_05_Carboplatin%20label%201-9-04%20FDA.pdf)

Carboplatin 10 mg/mL concentrate for infusion. Summary of Product Characteristics. April 2016 link: <http://www.medicines.org.uk/emcmobile/medicine/25716>

APPENDIX 5: Common Terminology Criteria for Adverse Events (CTCAE) –Version 4.03

The NCI CTCAE Version 4.03 (CTCAE 4.03 14 June 2010) can be accessed from the following National Cancer Institute (NCI) website:

<http://evs.nci.nih.gov/ftp1/CTCAE/About.html>

[http://evs.nci.nih.gov/ftp1/CTCAE/CTCAE\\_4.03\\_2010-06-14\\_QuickReference\\_5x7.pdf](http://evs.nci.nih.gov/ftp1/CTCAE/CTCAE_4.03_2010-06-14_QuickReference_5x7.pdf)

BOR	Best Overall Response
BPM	Beats Per Minute
BSA	Body Surface Area
BUN	Blood Urea Nitrogen
CBR	Clinical Benefit Rate
CDK	Cyclin Dependent Kinase
CI	Confidence Interval
CMH	Cochran-Mantel-Haenszel
CR	Complete Response
CSR	Clinical Study Report
CT	Computed Tomography
CTCAE	Common Terminology Criteria for Adverse Events
CV	Coefficient of Variation
DBP	Diastolic Blood Pressure
DMC	Data Monitoring Committee
DOR	Duration of Response
ECG	Electrocardiogram
ECOG	Eastern Cooperative Oncology Group
eCRF	Electronic Case Report Form
E/P/A	Etoposide, Carboplatin, and Atezolizumab
EOI	End of Infusion
ESA	Erythropoietin Stimulating Agent
████	████████████████████
██████	████████████████████████████████████
██████	██
G1T28	Trilaciclib
GCSF	Granulocyte Colony-Stimulating Factor
HR	Hazard Ratio
ICH	International Conference on Harmonization

Abbreviation	Term
irRECIST	immune-related Response Evaluation Criteria in Solid Tumors
ITT	Intent-to-treat
IV	Intravenous
LD	Longest Diameter
LDH	Lactate Dehydrogenase
LLN	Lower Limit of Normal Range
MAHE	Major Adverse Hematologic Event
MedDRA	Medical Dictionary for Regulatory Activities
mITT	Modified Intent-to-Treat
MRI	Magnetic Resonance Imaging
Nadir	The Lowest Point
NE	Not Evaluable
NLR	Neutrophil-Lymphocyte Ratio
NTL	Non-Target Lesion
OC	Observed Case
ORR	Objective Response Rate
PD	Progressive Disease
PFS	Progression-Free Survival
PFS2	Progression-Free Survival 2
PK	Pharmacokinetic
PLR	Platelet-Lymphocyte Ratio
PP	Per Protocol
PR	Partial Response
[REDACTED]	[REDACTED]
PT	Preferred Term
QOL	Quality of Life
RBC	Red Blood Cell
RECIST	Response Evaluation Criteria in Solid Tumors
RNA	Ribonucleic Acid
SAE	Serious Adverse Event
SAP	Statistical Analysis Plan
SBP	Systolic Blood Pressure
SCLC	Small Cell Lung Cancer
SD	Stable Disease
SOC	System Organ Class
SVN	Severe Neutropenia
TEAE	Treatment Emergent AE
TL	Target Lesion
TLFs	Tables, Listings, and Figures
TPR	Time Point Response
ULN	Upper Limit of Normal Range
WBC	White Blood Cell
WHO-DD	World Health Organization Drug Dictionary

1. INTRODUCTION

The purpose of this statistical analysis plan (SAP) is to describe the analyses to be performed following the completion of Study G1T28-05, Phase 2 Study of Carboplatin, Etoposide, and Atezolizumab With or Without Trilaciclib (G1T28) in Patients with Untreated Extensive Stage Small Cell Lung Cancer. The SAP is based on the G1T28-05 Protocol Version 3, dated 14 September 2018.

Study measurements and assessments, planned statistical methods, and derived variables are summarized in this plan. Planned tables, figures, and listings are specified. All decisions regarding final analyses, as defined in this SAP document, have been made prior to locking the database. Any deviations from these guidelines will be documented in the clinical study report (CSR).

1 of every 21-day cycles. Study drug refers to trilaciclib or placebo + E/P/A during the induction part and atezolizumab during the maintenance part. Treatment in both parts will continue until disease progression, unacceptable toxicity, withdrawal of consent, or discontinuation by investigator. Following disease progression per Response Evaluation Criteria in Solid Tumors, Version 1.1 (RECIST v1.1), if the patient appears to be deriving clinical benefit, the investigator believes it is in the best interest of the patient, and the patient has provided re-consent, study drug administration may be continued until loss of clinical benefit. The study includes 3 phases: Screening Phase, Treatment Phase (induction part + maintenance part), and Survival Follow-up Phase. The Treatment Phase begins on the day of first dose with study treatment and completes after the last Post Treatment Visit.

An independent data monitoring committee (DMC) will perform interim reviews of accumulating safety and disposition data approximately every 4 months during the Treatment Phase of the study, depending upon the enrollment rate. The first DMC meeting will occur after approximately the first 20 patients have been enrolled and completed at least 1 cycle. Details of the DMC, including objectives, composition, scope, and frequency, will be described in a DMC charter.

Criteria for Subsequent Cycles and Study Duration

Study drug administration will continue for up to 4 chemotherapy-containing (trilaciclib or placebo + E/P/A) cycles during the induction part of the study and atezolizumab monotherapy will be administered on Day 1 of every 21-day cycle during the maintenance part of the study. Study drug administration will continue until disease progression per RECIST v1.1, unacceptable toxicity, withdrawal of consent, or discontinuation by investigator, whichever occurs first. However, if the patient appears to be deriving clinical benefit, the investigator believes it is in the best interest of the patient, and the patient has provided re-consent, study drug administration may be continued until loss of clinical benefit (see Section 11.1.4). Treatment cycles will occur consecutively without interruption, except when necessary to manage toxicities or for administrative reasons as described below.

Criteria for Starting Cycle 2 and subsequent cycles in the induction part up to Induction Cycle 4

Patients must meet all of the following criteria:

- Absolute Neutrophil Count (ANC) $\geq 1.5 \times 10^9/L$
- Platelet count $\geq 100 \times 10^9/L$
- Nonhematologic drug-related toxicities (except alopecia) must be \leq Grade 1 or have returned to baseline

A delay of > 9 weeks for recovery from any toxicity related to trilaciclib or placebo + etoposide and carboplatin (E/P) in order to meet the continuation criteria will result in discontinuation of trilaciclib or placebo + E/P. A delay of > 15 weeks for recovery and management of immune-related toxicities attributed to atezolizumab (12 weeks for recovery to \leq Grade 1 and up to an additional 3 weeks for steroid taper of oral prednisone or equivalent to ≤ 10 mg/day) will result in discontinuation of atezolizumab. If patients meet the criteria for starting the subsequent cycle, a delay of up to 2 weeks is permitted for administrative reasons (eg, holiday, vacation, etc.);

however, a total delay of more than 9 weeks for trilaciclib or placebo + E/P, or 15 weeks for atezolizumab must be discussed with the medical monitor. [REDACTED]

[REDACTED]

[REDACTED]

[REDACTED]

[REDACTED]

Discontinuation or interruption of trilaciclib or placebo + E/P does not preclude continuation of atezolizumab and vice versa. For instance, if an AE is attributed to trilaciclib or placebo, etoposide, or carboplatin (eg, hematologic toxicity) during the induction part of the study; then atezolizumab may be continued while the trilaciclib or placebo + E/P are held. While the trilaciclib or placebo + E/P are held, the patient will continue to receive atezolizumab, be monitored for safety, and will begin the next trilaciclib or placebo + E/P/A-containing induction cycle after the toxicity resolves. If the AE is immune related and attributed to atezolizumab; then trilaciclib or placebo + E/P may be continued for up to 4 cycles while the atezolizumab is held.

After discontinuation of all study drugs, patients should be strongly encouraged to complete all scheduled assessments through the end of their current 21-day treatment cycle, [REDACTED]; CBC assessment on Day 22; all Post-Treatment Visits; and the Survival Follow-up Phase of the study, which is to continue until at least 70% of the patients on the study have died. The G1T28-05 study will be completed when the Survival Follow-up Phase has been completed, or upon sponsor termination of the study.

- The total study duration is at least 36 months, assuming 12 months of accrual and 24 months follow-up.
- The Survival Follow-up Phase will continue until at least 70% of the randomized patients have died.

The study scheduled assessments are presented in [Table 2](#) below:

Table 2 Schedule of Assessments

Cycle Day	Screening	Enroll	Induction (21-day cycles) ^a										Last Induction Cycle	Maintenance (21-day cycles) ^b		Post-Treatment Visits ^c		Survival Follow-up ^d
			Induction Cycles 1 and 3					Induction Cycles 2 and 4						Maintenance Cycle 1 and Odd Cycles	Maintenance Cycle 2 and Even Cycles	30 (+3)	90 (+7)	
	-14	-3 to 1	1	2	3	8	15	1	2	3	8	15	22	1	1	30 (+3)	90 (+7)	
Informed Consent ^e	X																	
Demographics	X																	
Medical History ^f	X																	
Eligibility Eval.	X	X																
Performance Status	X		X					X						X	X	X	X	
Physical Exam	X		X					X						X	X	X	X	
Height, Weight & Vital Signs ^g	X		X		X			X		X				X	X	X	X	
Electrocardiogram	X												X					
Clinical Chemistry	X		X ^h					X ^h						X ^h	X ^h	X	X	
TSH, free T4, and free T3	X							X							X	X	X	
Hematology	X		X ⁱ		X	X	X	X ⁱ		X	X	X	X	X ⁱ	X ⁱ	X	X	
Urinalysis	X		X ^h					X ^h						X ^h	X ^h	X	X	
Pregnancy test ^j		X ^j														X	X	
Randomization ^k		X																
Tumor Assessment ^l	X ^{l2}											X			X	X ^{l1,l2}	X ^{l1,l2}	X ^{l1}
Archived Tumor Sample ^m		X																
Trilaciclib or Placebo ⁿ			X	X	X			X	X	X								
Carboplatin			X					X										
Etoposide			X	X	X			X	X	X								
Atezolizumab			X ^o					X ^o						X	X			
██████████ ██████████			■					■						■	■	■	■	
PK ^q (Trilaciclib, Etoposide, Carboplatin)			X															

	Screening	Enroll	Induction (21-day cycles) ^a										Last Induction Cycle	Maintenance (21-day cycles) ^b		Post-Treatment Visits ^c		Survival Follow-up ^d
			Induction Cycles 1 and 3					Induction Cycles 2 and 4						Maintenance Cycle 1 and Odd Cycles	Maintenance Cycle 2 and Even Cycles			
Cycle Day	-14	-3 to 1	1	2	3	8	15	1	2	3	8	15	22	1	1	30 (+3)	90 (+7)	
Atezolizumab PK ^r			X					X							X	X	X	
Immunologic Marker ^s			X ^s											X ^s			X ^s	
██████████ ██████████			■					■							■	■	■	
AEs ^u	X ^u												X ^u				X ^u	
Con. Medications	X												X					
Survival Follow-up ^d																		X

AE = adverse event; Eval. = evaluation; ██████████

██████████ irRECIST = immune-related RECIST; ██████████; PK = pharmacokinetics; RECIST v1.1 = Response Evaluation

Criteria in Solid Tumors, Version 1.1; T3 = tri-iodothyronine; T4 = thyroxine; TSH = thyroid-stimulating hormone

a During the induction part, study drug administration (trilaciclib or placebo plus E/P/A) will continue for up to four 21-day cycles or until disease progression per RECIST v1.1, unacceptable toxicity, withdrawal of consent, or discontinuation by investigator, whichever occurs first. Following disease progression per RECIST v1.1, if the patient appears to be deriving clinical benefit, the investigator believes it is in the best interest of the patient, and the patient has provided re consent, study drug administration may be continued until loss of clinical benefit.

b During the maintenance part, study drug administration (atezolizumab) will continue in 21-day cycles until disease progression per RECIST v1.1, unacceptable toxicity, withdrawal of consent, or discontinuation by investigator, whichever occurs first. Following disease progression per RECIST v1.1, if the patient appears to be deriving clinical benefit, the investigator believes it is in the best interest of the patient, and the patient has provided re consent, study drug administration may be continued until loss of clinical benefit.

c Patients will return to the study center for post-treatment visits at 30 (+3) and 90 (+7) days after the last dose of study drug.

d Monthly phone calls will be made to each patient that is in the Survival Follow-up Phase. Patients will be followed for survival until at least 70% of the patients have died. Any anticancer therapies used will be collected.

e Informed consent may be obtained up to 28 days prior to the first study treatment administration.

f Including medical, surgical, radiation history, smoking history, family history, documentation of tumor diagnosis, baseline signs and symptoms within 4 weeks prior to randomization, weight loss in the 6 months prior to randomization (≤ 5% or > 5%), and medications taken within 14 days of enrollment.

g Height will only be measured at the screening visit. Weight will only be measured at the screening visit and on Day 1 of each cycle. Body surface area calculation (based on actual body weight) will be completed on Day 1 of each cycle and vital signs obtained within 15 minutes before and after trilaciclib or placebo and E/P/A infusions. Vitals only need to be taken before the trilaciclib or placebo infusion, between each subsequent infusion, and after the last infusion on Days 1 and 3.

h Clinical chemistry (albumin, alkaline phosphatase, total bilirubin, calcium, chloride, creatinine, glucose, inorganic phosphorus, potassium, total protein, ALT, AST, lactate dehydrogenase [LDH], sodium, and blood urea nitrogen [BUN], amylase, lipase) and urine analysis may be obtained up to 72 hours prior to the first dose of each cycle of trilaciclib or placebo + E/P/A therapy (induction part) or atezolizumab (maintenance part).

i Hematology will be obtained (hemoglobin, white blood cells (WBC) with differential, and platelet counts). Hematology may be obtained up to 24 hours prior to first dose of each cycle of trilaciclib/placebo + E/P/A therapy (induction part) or atezolizumab (maintenance part).

j For female patients of childbearing potential: serum β-hCG at enrollment; and serum or urine β-hCG obtained at the post-treatment visits.

k Randomization is to be done within 3 days prior to first dose of trilaciclib or placebo + E/P/A therapy, following confirmation that the patient is eligible for the study.

l For tumor assessment, all sites of disease should be assessed radiologically by CT or MRI at screening and after every even cycle for 9 months of the study (ie, approximately every 6 weeks) and after every third cycle (ie, approximately every 9 weeks) thereafter while receiving study drug, until the occurrence of disease progression. Additional scans may be obtained at the discretion of the investigator, if clinically indicated. If a patient shows a radiological response (CR or PR), a confirmatory radiological assessment will be performed at least 4 weeks after the response was first noted. Assessments should be performed within 7 days of starting the subsequent cycle. The same method of assessment (CT or MRI) should be used to characterize tumors at screening and at all follow-up assessments. If positron emission tomography is used, it should also be accompanied by spiral CT or MRI.

l1: At the post-treatment visits at 30 (+3) and 90 (+7) days after the last dose of study drug, obtain tumor assessment for patients who have not progressed at the time of study drug discontinuation (may be performed within 4 weeks). For those patients in the survival follow-up who have not progressed at the time of study drug discontinuation, tumor assessments, including all sites of disease, will be assessed radiologically by CT or MRI, as performed at screening, every 2 months (approximately 60 ± 7 days) until the occurrence of progressive disease or study completion.

l2: Brain scans with contrast (by CT or MRI) to be obtained with tumor assessment at screening (within 28 days of dosing). Patients without the presence of brain metastases at screening should also have a brain scan at the end of the induction part. Patients with brain metastases at screening should have brain scans with every scheduled tumor assessment.

m Archived tumor samples should be available for banking for assessment of relevant DNA, ribonucleic acid (RNA), and protein markers, such as PD-L1 or those involved in the CDK4/6 pathway. Tumor samples may be banked for up to 10 years.

n Trilaciclib or placebo will be administered as an IV infusion in 250 mL of D5W or sodium chloride solution 0.9% over approximately 30 minutes prior to E/P chemotherapy on Days 1 to 3 of every induction cycle. If there is any volume remaining in the trilaciclib or placebo infusion bag at the end of the 30 minutes, the infusion should be continued at the same rate until the entire contents of the bag have been administered to ensure patients receive the full dose. The interval between doses of trilaciclib or placebo on successive days should not be greater than 28 hours. The interval between the dose of trilaciclib or placebo and the first dose of chemotherapy on a given day (etoposide or carboplatin) should not be greater than 4 hours. Trilaciclib or placebo will only be administered with chemotherapy. If administration of E/P chemotherapy is discontinued, trilaciclib or placebo should also be discontinued. Chemotherapy cannot be administered until after completion of the trilaciclib or placebo infusion. If the second or third dose of trilaciclib in any given cycle is not administered for any reason, do not administer the dose of etoposide or carboplatin chemotherapy on that day. After discontinuation of study drug, patients should be strongly encouraged to complete all scheduled assessments through the end of their current 21-day treatment cycle, [REDACTED]

o [REDACTED] CBC assessment on Day 22; the Post-Treatment Visits; and the Survival Follow-up Phase of the study.

p During the induction part, atezolizumab should be administered following the administration of trilaciclib or placebo, etoposide, and carboplatin.

q At least 5 patients enrolled in each treatment group will have trilaciclib, etoposide, and carboplatin PK samples collected on Day 1 of Induction Cycles 1 and 3 at the time points specified.

r Blood samples will be collected from all patients predose and 30 minutes after the end of atezolizumab infusion to determine the minimum and maximum observed serum atezolizumab concentration on Day 1 of Induction Cycles 1, 2, 3, and 4; Maintenance Cycles 4, 8, 12, and every eighth cycle thereafter; and at 30 (+3) and 90 (+7) days after the last dose of study drug.

s Peripheral blood samples will be collected at predose on Day 1 of Induction Cycle 1, Day 1 of Maintenance Cycle 1 (first cycle of maintenance part), Day 1 of Maintenance Cycle 5, and at the post treatment visit at 90 (+7) days after the last dose of study drug.

t [REDACTED]

u Adverse events will be recorded from the time of informed consent. AEs will be collected through 30 days after the last dose of study drug; SAEs and AESI will be collected through 90 days after the last dose of study drug. All AEs should be followed until they are resolved, have returned to baseline, or it is deemed that further recovery is unlikely.

2.3. Number of Patients

Overall, approximately 100 patients will be enrolled in the study. The 100 patients will be randomly assigned (1:1 fashion) to trilaciclib 240 mg/m² or placebo administered IV on Days 1 to 3 with E/P/A therapy for up to four 21-day cycles (induction part).

The initial sample size calculations were based on a primary endpoint of OS where a sample size of 100 (1:1 treatment allocation ratio between the two groups of placebo + E/P/A and trilaciclib + E/P/A) provided 80% power to detect a hazard ratio of 0.6 using an overall type 1 error probability of 0.1 (1-sided). With the change in endpoints outlined in amendment 2, the sample size calculation is now based on demonstrating the superiority of trilaciclib + E/P/A versus placebo + E/P/A with respect to at least one of the primary endpoints. With this amendment, the overall type I error rate is now 0.025 (1-sided) and the type II error rate used to compute sample size is 0.10 (corresponding to 90% power).

To maintain the overall type I error rate, by using the most conservative Bonferroni procedure for the 2 primary endpoints, a 1-sided individualized type I error rate $0.025/2 = 0.0125$ is assigned to each outcome variable in the sample size calculation. Assuming a common standard deviation of 2.5, a true difference in the duration of severe (Grade 4) neutropenia in Cycle 1 of at least 2 days between the treatment groups (trilaciclib + E/P/A versus placebo + E/P/A) requires 82 evaluable patients (41 per treatment arm). This implies that 88 patients need to be randomized assuming a 95% evaluability rate. For occurrence endpoints (occurrence of severe (Grade 4) neutropenia, assuming its proportion of 45% for placebo + E/P/A, testing for an absolute reduction of 34% to 11% with trilaciclib + E/P/A would require a sample size of at least 100 patients (50 per treatment arm). Assuming a 95% evaluability rate, at least 106 patients need to be enrolled to complete the study. Therefore, the final adjusted sample size is 106 to account for the evaluation of 2 primary endpoints.

All calculations were carried out using the POWER procedure in SAS® version 9.4.

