	Evaluate potential of trilaciclib to reduce chemotherapy-induced myelosuppression by assessing effects on multiple lineages and current standard of care interventions to treat myelosuppression (neutrophils, RBC, platelets, lymphocytes)
	Describe the PK of trilaciclib, carboplatin, and etoposide in a subset of patients; and atezolizumab in all patients
[REDACTED]	
[REDACTED]	
[REDACTED]	
[REDACTED]	
[REDACTED]	
[REDACTED]	
[REDACTED]	
[REDACTED]	

ATA = anti-atezolizumab therapeutic antibodies; irRECIST = immune-related Response Evaluation Criteria in Solid Tumors; E/P/A = etoposide/carboplatin/atezolizumab; ORR = objective response rate; OS = overall survival; PFS = progression-free survival; PK = pharmacokinetics; [REDACTED] RBC = red blood cells; SCLC = small cell lung cancer

Study Design	This is a randomized, double-blind, placebo-controlled, multicenter, Phase 2 study of the efficacy and safety of E/P/A with trilaciclib or placebo therapy for patients with newly diagnosed extensive-stage SCLC. Approximately 100 patients will be randomly assigned (1:1 fashion) to trilaciclib or placebo administered intravenously on Days 1 to 3 with E/P/A therapy for up to four 21-day cycles (induction part). Following the completion of up to 4 chemotherapy-containing (trilaciclib or placebo +
--------------	---

---

E/P/A) cycles, patients will proceed to the maintenance part of the study and receive atezolizumab every 21 days. Study drug refers to trilaciclib or placebo + E/P/A during the induction part and atezolizumab during the maintenance part. Treatment in both parts will continue until disease progression, unacceptable toxicity, withdrawal of consent, or discontinuation by investigator. Following disease progression per RECIST v1.1, if the patient appears to be deriving clinical benefit, the investigator believes it is in the best interest of the patient, and the patient has provided re-consent, study drug administration may be continued until loss of clinical benefit. The study includes 3 phases: Screening Phase, Treatment Phase (induction part + maintenance part), and Survival Follow-up Phase. The Treatment Phase begins on the day of first dose with study treatment and completes after the last Post-Treatment Visit. Randomization will be stratified by Eastern Cooperative Oncology Group (ECOG) performance status (0 to 1 versus 2) and presence of brain metastases (yes versus no).

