#### **Treatment Duration**

Study drug administration will continue for each patient until disease progression per RECIST v1.1, unacceptable toxicity, withdrawal of consent, or discontinuation by investigator, whichever occurs first. However, if the patient appears to be deriving clinical benefit, the investigator believes it is in the best interest of the patient, and the patient has provided re-consent, study drug administration may be continued until loss of clinical benefit.

Study drug refers to trilaciclib or placebo + E/P/A during the induction part and atezolizumab during the maintenance part.

---

---

Study Duration	
The total study duration is at least 36 months, assuming 12 months of accrual and 24 months follow-up.
 
The Survival Follow-up Phase will continue until at least 70% of the randomized patients have died.

Approximate Number of Patients	
Approximately 100 patients will be randomly assigned to 1 of 2 groups as follows: trilaciclib administered intravenously (IV) with E/P/A therapy during induction followed by atezolizumab maintenance (Group 1) or placebo administered IV with E/P/A therapy during induction followed by atezolizumab maintenance (Group 2).

Number of Study Centers	
Up to 60 centers in North America and Europe

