Pharmacokinetic parameters will be calculated using noncompartmental methods based on the plasma concentration-time data. Pharmacokinetic parameters will be summarized descriptively.

---

Rationale for Number of Patients

The sample size calculation is based on demonstrating the superiority of trilaciclib + E/P/A versus placebo + E/P/A for the primary endpoints. To maintain the overall type I error rate using the most conservative Bonferroni procedure for the 2 primary endpoints, a 1-sided individualized type I error rate  $0.025/2 = 0.0125$  is assigned to each outcome variable in the sample size calculation. Assuming a 95% evaluability rate, at least 106 patients need to be enrolled to complete the study.

---

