## 6. INVESTIGATIONAL PLAN

### 6.1. Overall Study Design and Plan

This is a randomized, double-blind, placebo-controlled, multicenter, Phase 2 study of the efficacy and safety of E/P/A with trilaciclib or placebo therapy for patients with newly diagnosed extensive-stage SCLC. Approximately 100 patients will be randomly assigned (1:1 fashion) to trilaciclib 240 mg/m^2 or placebo administered IV on Days 1 to 3 with E/P/A therapy for up to four 21-day cycles (induction part) (Figure 6-1). Randomization will be stratified by Eastern Cooperative Oncology Group (ECOG) performance status (0 to 1 versus 2) and presence of brain metastases (yes versus no). Following the completion of up to 4 chemotherapy-containing (trilaciclib or placebo + E/P/A) cycles, patients will proceed to the maintenance part of the study and receive atezolizumab every 21 days. Study drug refers to trilaciclib or placebo + E/P/A during the induction part and atezolizumab during the maintenance part. Treatment in both parts will continue until disease progression, unacceptable toxicity, withdrawal of consent, or discontinuation by investigator. Following disease progression per RECIST v1.1, if the patient appears to be deriving clinical benefit, the investigator believes it is in the best interest of the patient, and the patient has provided re-consent, study drug administration may be continued until loss of clinical benefit. The study includes 3 phases: Screening Phase, Treatment Phase (induction part + maintenance part), and Survival Follow-up Phase. The Treatment Phase begins on the day of first dose with study treatment and completes after the last Post Treatment Visit.

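### The plan gives two enrolment figures, about 100 and at least 106, and presents power for each primary endpoint as power for at least one of them

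*SAP*

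**What the plan says.** **Enrolment figure.** SAP 2.3 opens with "Overall, approximately 100 patients will be enrolled in the study" and goes on to say that these 100 are randomised 1:1. The same section later derives at least 106 and ends: "Therefore, the final adjusted sample size is 106 to account for the evaluation of 2 primary endpoints".

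The protocol carries both figures:
- About 100: the synopsis under Study Design and under Approximate Number of Patients ("Approximately 100 patients will be randomly assigned to 1 of 2 groups as follows"), section 6.1, and section 7.1.
- 106: the synopsis under Rationale for Number of Patients ("Assuming a 95% evaluability rate, at least 106 patients need to be enrolled to complete the study"), and section 13.1.

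**Meaning of the 90%.** SAP 2.3 and protocol 13.1 say the calculation aims at superiority "with respect to at least one of the primary endpoints", with 90% power. The next paragraph of each gives every primary endpoint a one-sided 0.0125 by Bonferroni, sizes the two separately and keeps the larger number. The synopsis states the goal differently: "demonstrating the superiority of trilaciclib + E/P/A versus placebo + E/P/A for the primary endpoints".

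**Testing rule.** SAP 6.2.7.1.4 tests duration of severe neutropenia in Cycle 1 first, and occurrence of severe neutropenia only if the first is significant. Protocol 13.5.3.2 says that under this Region 2 strategy the study can potentially be called positive if at least both are significant.

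**The concern.** Both enrolment figures are operative text, not entries in an amendment log. Protocol section 13 lets the SAP override the protocol where analyses differ, but that does not settle the target, because both figures stand in SAP 2.3. A floor of 106 is not met by 100, even with the word approximately attached. If enrolment stopped between 100 and 105, the plan would support two answers on whether the target had been reached.

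The power statement is a separate matter. The chance of winning at least one of two endpoints is a different quantity from the chance of winning each one. A reader who takes the 90% at its label will quote a probability for an event that was not calculated.

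**Working it through.** **Inputs** (SAP 2.3, repeated in protocol 13.1): one-sided alpha 0.0125 per endpoint; 90% power; duration difference 2 days, SD 2.5; occurrence 45% versus 11%; 1:1 allocation; 95% evaluable. The documents name the SAS POWER procedure but not the test behind each figure.

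**1. Reproducing the plan's numbers**
- *Duration, two-sample t-test.* Noncentrality is 2 / (2.5 × √(2/n)). At n = 41 per arm this is 3.62 on 80 df, with power 90.7%. This matches 82 evaluable.
- *Occurrence, log-odds-ratio formula.* n per arm = (z₀.₉₈₇₅ + z₀.₉₀)² × [1/(0.45×0.55) + 1/(0.11×0.89)] / (ln OR)². The odds ratio is (0.45×0.89)/(0.11×0.55) = 6.62, and ln OR = 1.890. So n = (2.241 + 1.282)² × 14.25 / 1.890² = 49.5, rounded up to 50. Power at 50 is Φ(1.890/√(14.25/50) − 2.241) = 90.3%. This matches 100 evaluable.
- Other two-proportion methods need fewer per arm: 41 (pooled normal), 46 (exact Fisher), 47 (continuity-corrected). The log-odds-ratio basis is therefore inferred from the match.
- *Inflation.* 41/0.95 = 43.2, so 44 per arm, or 88. 100/0.95 = 105.3, so 106.

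All four stated numbers (82, 88, 100, 106) reproduce.

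**2. What the two enrolment figures deliver at 95% evaluable**
- 100 × 0.95 = 95, about 47 per arm, which is 5 short of the 100 evaluable required.
- 106 × 0.95 = 100.7, or 50 per arm.

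The figure 100 coincides both with the superseded size based on overall survival and with the evaluable number for occurrence.

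**3. What the 90% describes**

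Step 1 gives about 90% for each endpoint alone. Power for at least one endpoint cannot be below the larger single power, whatever the correlation. At 50 per arm and one-sided 0.0125, duration alone has 95.6%, so power for at least one is at least 95.6%.

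**4. The Region 2 sequence (context only)**

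Each of the first two families holds one hypothesis. The SAP's truncated Hochberg threshold, [γ + (1−γ)/m]α with m = 1, equals α for any γ, so each test uses the full 0.025. The probability of rejecting both is at least P₁ + P₂ − 1 and at most the smaller of the two. Duration power at 0.025 is 97.0% (47 per arm) and 97.7% (50 per arm).

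| Test used for occurrence | Power, 47 / 50 per arm | Lower bound for both, 47 / 50 per arm |
|---|---|---|
| Log-odds-ratio formula | 92.9% / 94.3% | 89.9% / 92.0% |
| Exact Fisher | 95.3% / 96.5% | 92.3% / 94.3% |
| Log-risk-ratio Wald, enumerated | 96.2% / 97.1% | 93.2% / 94.8% |

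Bounds use unrounded powers. These are substitute tests; the planned models are nonparametric ANCOVA and modified Poisson regression (SAP 6.2.7.1.1).

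**The case against.** The best defence is that the intended target is clear. SAP 2.3 and protocol 13.1 derive 106 step by step and call it final, the synopsis rationale agrees, and both sections identify 100 as the older size based on survival. That largely stands. A reader might infer that the planned number cannot be determined, but the documents do not support going that far. What remains is that the lower figure is still written as an instruction in five places.

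On power, the paragraph after the label discloses the Bonferroni split and the separate sizing. Sizing each endpoint for 90% does guarantee at least 90% for at least one. This also stands: the label is imprecise and errs on the conservative side.

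The 5% loss may not apply in full. The ITT set is all randomised patients (SAP 3.1.1), and a patient without an observed event counts as No (SAP 5.1.1.1), so 100 randomised might supply 50 per arm for occurrence. Against that, SAP 6.1.2 excludes missing data from efficacy analyses, and the plan itself applies the 95%. The shortfall of 5 is a shortfall on the plan's own terms.

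A reader might also infer that the trial is underpowered, or that the Region 2 sequence is. Neither follows. Sizing at 0.0125 is stricter than the 0.025 the sequence uses, and the lower bounds in step 4 are about 90% or more at either enrolment figure. The absence of a stated power for the sequence is missing detail, not an error.

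**Conclusion.** Two corrections are warranted.

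First, the plan states two enrolment figures that differ by 6 patients. The lower leaves about 95 evaluable on the plan's own 95% assumption, against the 100 it requires. The derivation supports 106.

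Second, the 90% is power for each primary endpoint at one-sided 0.0125 (90.7% at 41 per arm; 90.3% at 50 per arm). Power for at least one endpoint at 50 per arm is at least 95.6%.

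The second result assumes a t-test for duration and, for occurrence, a log-odds-ratio formula inferred because it reproduces 50. For that reason no single power figure for 100 randomised patients is offered as the plan's own. The 95.6% rests on the duration t-test alone and holds for any correlation between the endpoints.

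The arithmetic behind 106 is sound, and no shortfall in power is shown.

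**What to change.** 1. Replace about 100 with 106 in SAP 2.3 (opening paragraph), the protocol synopsis (Study Design; Approximate Number of Patients), and protocol 6.1 and 7.1. If the sponsor keeps 100 as the number randomised, it should withdraw the 106 statements and restate the power from its own POWER procedure settings, naming the test.
2. In SAP 2.3 and protocol 13.1, say that 90% is the power for each primary endpoint at one-sided 0.0125. Align the synopsis rationale with that sentence.
3. Optional: for the Region 2 sequence, add the sponsor's own power to reject both primary hypotheses at one-sided 0.025 each, computed under the planned models. The substitute-test lower bounds (about 90–93% at 47 per arm, 92–95% at 50) are a guide and should not be inserted as they stand.

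Items 1 and 2 cost wording only if 106 is used, or one recalculation if 100 is kept. Item 3 costs one calculation. None changes the design or the alpha.
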